#### *Toxicity*

Virtually all phase I and II studies of irinotecan have reported neutropenia and/or late diarrhea (diarrhea occurring more than 24 hours after the irinotecan administration as the dose limiting toxicities (depending on the schedule). Other commonly observed adverse events include nausea and vomiting, anorexia, abdominal cramping, alopecia, asthenia, lymphocytopenia, and anemia. Dehydration has occurred as a consequence of diarrhea, particularly when associated with severe vomiting. Patients may have an acute syndrome of lacrimation, diaphoresis, abdominal cramping, and diarrhea (early diarrhea) during or shortly after irinotecan administration; this syndrome is thought to be cholinergically mediated, and may be treated and subsequently prevented with atropine. Sporadic cases of pulmonary toxicity, manifested as shortness of breath, non-productive cough and transient infiltrates on chest x-ray have been reported. Infrequent occurrences of mucositis or colitis (sometimes with gastrointestinal bleeding) have been observed. Occasionally, abnormalities of serum creatinine, hepatic enzymes, or thrombocytopenia have been observed.

Please refer to the package insert for further information regarding irinotecan. Of note, concerns related to adverse effects:

- Bone marrow suppression: [U.S. Boxed Warning]: May cause severe myelosuppression. Deaths due to sepsis following severe myelosuppression have been reported. Therapy should be temporarily discontinued if neutropenic fever occurs or if the absolute neutrophil count is  $<1000/\text{mm}^3$ . The dose of irinotecan should be reduced if there is a clinically significant decrease in the total WBC ( $<200/\text{mm}^3$ ), neutrophil count ( $<1500/\text{mm}^3$ ), hemoglobin ( $<8 \text{ g/dL}$ ), or platelet count ( $<100,000/\text{mm}^3$ ). Routine administration of a colony-stimulating factor is generally not necessary, but may be considered for patients experiencing significant neutropenia.
- Colitis: Colitis, complicated by ulceration, bleeding, ileus, and infection has been reported.
- Diarrhea: [U.S. Boxed Warning]: Severe diarrhea may be dose-limiting and potentially fatal; two severe (life-threatening) forms of diarrhea may occur. Early diarrhea occurs during or within 24 hours of receiving irinotecan and is characterized by cholinergic symptoms (eg, increased salivation, diaphoresis, abdominal cramping); it is usually responsive to atropine. Late diarrhea occurs more than 24 hours after treatment which may lead to dehydration, electrolyte imbalance, or sepsis; it should be promptly treated with loperamide. Patients with diarrhea should be carefully monitored and treated promptly.
- Hypersensitivity reactions: Severe hypersensitivity reactions have occurred.
- Renal toxicity: Renal impairment and acute renal failure have been reported, possibly due to dehydration secondary to diarrhea.

Disease-related concerns:

- Bowel obstruction: Patients with bowel obstruction should not be treated with irinotecan until resolution of obstruction.
- Hepatic impairment: Use with caution in patients with hepatic impairment.
- Hyperbilirubinemia: Patients with even modest elevations in total serum bilirubin levels (1-2 mg/dL) have a significantly greater likelihood of experiencing first-course grade 3 or 4 neutropenia than those with bilirubin levels that were  $<1 \text{ mg/dL}$ . Patients with abnormal glucuronidation of bilirubin, such as those with Gilbert's syndrome, may also be at greater risk of myelosuppression when receiving therapy with irinotecan. Use caution when treating patients with known hepatic dysfunction or hyperbilirubinemia; dosage adjustments should be considered.

## 10. STUDY CALENDAR

Baseline evaluations are to be conducted within 1 week prior to start of protocol therapy. Scans and x-rays must be done  $\leq 2$  weeks prior to the start of therapy. In the event that the patient's condition is deteriorating, laboratory evaluations should be repeated within 48 hours prior to initiation of the next cycle of therapy. Radiographic evaluation must include cross-sectional imaging of the chest, abdomen and pelvis. Options include CT chest/abdomen/pelvis with intravenous contrast, or MRI abdomen/pelvis with intravenous contrast along with CT chest with or without intravenous contrast. Scans will be performed every 8 weeks. In cases of treatment delays, efforts will be made to maintain scans at every 8 week +/- 2 week intervals regardless of the cycle number. For all the visits and related procedures, a 7 days window from the anticipated treatment date will be permitted if necessary to accommodate any necessary date modifications. The schedule below illustrates calendar for 1st 12 weeks.

	Pre-Study (within 2 weeks cycle 1)	C 1	C 2	C 3	C 4	C 5	C 6	C 7	C 8	C 9	C 10	C 11	C 12	Maintenance treatment c Or Off treatment/ study
Informed consent	X													
Demographics	X													
Medical history	X	X	X		X	X		X		X		X	X	X
Concurrent meds	X	X	X	X	X	X	X	X	X	X	X	X	X	X
Physical exam	X	X	X	X		X		X				X		X
Vital signs	X	X	X	X	X	X	X	X	X			X		X
Height	X													
Weight	X	X	X	X		X		X		X		X		X
Performance status	X	X	X	X		X		X		X		X	X	X
CBC w/diff, plts	X	X	X	X	X	X	X	X	X	X	X	X	X	
Chemistry a	X	X	X	X	X	X	X	X	X	X	X	X	X	
B-HCG b	X													
Adverse event evaluation		X	X	X	X	X	X	X	X	X	X	X	X	X
Tumor measurements d	X					X				X			X	X

A: Albumin, alkaline phosphatase, total bilirubin, bicarbonate, BUN, calcium, chloride, creatinine, glucose, potassium, total protein, SGOT [AST], SGPT [ALT], sodium.

b: Serum pregnancy test (women of childbearing potential).

c: after 12 cycles patient will be allowed to continue on a maintenance treatment per investigators discretion.

d: CT chest/abdomen/pelvis, or MRI abdomen/pelvis with CT chest. Tumor/radiological measurements are repeated every 8 weeks +/- 2 weeks. Documentation (radiologic) must be provided for patients removed from study for progressive disease. Patients on maintenance, off-treatment and/or study will be scanned every 8 weeks as part of routine follow-up.

## **Long Term/Survival Follow-up Procedures**

### **Discontinuation of Therapy**

The Investigator will withdraw a patient whenever continued participation is no longer in the patient's best interests. Reasons for withdrawing a patient include, but are not limited to, disease progression, the occurrence of an adverse event or a concurrent illness, a patient's request to end participation, a patient's non-compliance or simply significant uncertainty on the part of the Investigator that continued participation is prudent. There may also be administrative reasons to terminate participation, such as concern about a patient's compliance with the prescribed treatment regimen.

## **11. MEASUREMENT OF EFFECT**

The primary efficacy endpoint is objective response rate as determined by radiology review.

### **11.1 RECIST Criteria for response**

The Response Evaluation Criteria in Solid Tumors (RECIST 1.1) guidelines will be employed in this study. For the purposes of this study, measurable disease is defined as the presence of at least one measurable lesion. Measurable lesions must be accurately measured in at least one dimension (longest diameter in the plane of measurement is to be recorded) with a minimum size of:

- 10 mm by CT scan (CT scan slice thickness no greater than 5 mm; when CT scans have slice thickness >5 mm, the minimum size should be twice the slice thickness).
- 10 mm caliper measurement by clinical exam (lesions which cannot be accurately measured with calipers should be recorded as non-measurable).
- 20 mm by chest X-ray.

To be considered pathologically enlarged and measurable, a lymph node must be =15 mm in short axis when assessed by CT scan (CT scan slice thickness is recommended to be no greater than 5 mm). At baseline and in follow-up, only the short axis will be measured and followed.

Lytic bone lesions or mixed lytic-blastic lesions with identifiable soft tissue components that can be evaluated by cross-sectional imaging techniques such as CT or MRI can be considered measurable if the soft tissue component meets the definition of measurability described above.

'Cystic lesions' thought to represent cystic metastases can be considered measurable if they meet the definition of measurability described above. However, if non-cystic lesions are present in the same patient, these are preferred for selection as target lesions.

Non-measurable lesions: all other lesions, including small lesions (longest diameter <10 mm or pathological lymph nodes with 10 to <15 mm short axis), as well as truly non-measurable lesions. Lesions considered truly non-measurable include: leptomeningeal disease, ascites, pleural or pericardial effusion, inflammatory breast disease, lymphangitic involvement of skin or lung, abdominal masses/abdominal organomegaly identified by physical exam that is not measurable by reproducible imaging techniques. Blastic bone lesions are non-measurable. Lesions with prior local treatment, such as those situated in a previously irradiated area or in an area subjected to other loco-regional therapy, are not considered measurable unless there has been demonstrated progression (by RECIST 1.1) in the lesion.

Target lesions: all measurable lesions up to a maximum of two lesions per organ and five lesions in total, representative of all involved organs, should be identified as target lesions and will be recorded and measured at

baseline. Target lesions should be selected on the basis of their size (lesions with the longest diameter) and their suitability for accurate repetitive measurements (either by imaging techniques or clinically). A sum of the diameters (longest for non-nodal lesions, short axis for nodal lesions) for all target lesions will be calculated and reported as the baseline sum diameters. The baseline sum diameters will be used as reference to further characterize the objective tumor response of the measurable dimension of the disease. If lymph nodes are to be included in the sum, only the short axis will contribute.

**Non-target lesions:** All lesions (or sites of disease) not identified as target lesions, including pathological lymph nodes and all non-measurable lesions, should be identified as non-target lesions and be recorded at baseline. Measurements of these lesions are not required and they should be followed as 'present', 'absent' or in rare cases, 'unequivocal progression'.

### **11.1.1 Evaluation of target lesions**

**Complete response (CR):** complete disappearance of all target lesions, confirmed by repeat assessments at no less than 4 weeks after the criteria for response are first met. Any pathological lymph nodes (whether target or non-target) must have reduction in short axis to  $<10$  mm

**Partial response (PR):** at least a 30% decrease in the sum of diameters of target lesions, taking as reference the baseline sum longest diameter. This must be confirmed by repeat assessment at no less than 4 weeks after the criteria for response are first met.

**Progressive disease (PD):** at least a 20% increase in the sum of diameters of target lesions, taking as reference the smallest sum on study (this may include the baseline sum). The sum must also demonstrate an absolute increase of at least 5 mm.

**Stable Disease (SD):** neither sufficient decrease to qualify for partial response nor sufficient increase to qualify for progressive disease.

### **11.1.2 Special notes on the assessment of target lesions**

- Lymph nodes identified as target lesions should always have the actual short axis measurement recorded even if the nodes regress to below 10 mm on study. When lymph nodes are included as target lesions, the 'sum' of lesions may not be zero even if complete response criteria are met since a normal lymph node is defined as having a short axis of  $<10$  mm.
- Target lesions that become 'too small to measure'. While on study, all lesions (nodal and non-nodal) recorded at baseline should have their actual measurements recorded at each subsequent evaluation, even when very small. However, sometimes lesions or lymph nodes become so faint on a CT scan that the radiologist may not feel comfortable assigning an exact measure and may report them as being 'too small to measure', in which case a default value of 5 mm should be assigned.
- Lesions that split or coalesce on treatment. When non-nodal lesions 'fragment', the longest diameters of the fragmented portions should be added together to calculate the target lesion sum. Similarly, as lesions coalesce, a plane between them may be maintained that would aid in obtaining maximal diameter measurements of each individual lesion. If the lesions have truly coalesced such that they are no longer separable, the vector of the longest diameter in this instance should be the maximal longest diameter for the 'coalesced lesion'.

### **11.1.3 Evaluation of non-target lesions**

**Complete Response (CR):** Disappearance of all non-target lesions and normalization of tumor marker levels. All lymph nodes must be non-pathological in size ( $<10$  mm short axis).

**Non-CR / Non-PD:** Persistence of one or more non-target lesion(s) and/or maintenance of tumor marker levels above normal limits.

Progressive Disease (PD): Unequivocal progression of existing non-target lesions.

- When patient has measurable disease. To achieve ‘unequivocal progression’ on the basis of the non-target disease, there must be an overall level of substantial worsening in non-target disease such that, even in presence of SD or PR in target disease, the overall tumor burden has increased sufficiently to merit discontinuation of therapy. A modest ‘increase’ in the size of one or more non-target lesions is usually not sufficient to qualify for unequivocal progression status.
- When patient has only non-measurable disease. There is no measurable disease assessment to factor into the interpretation of an increase in non-measurable disease burden. Because worsening in non-target disease cannot be easily quantified, a useful test that can be applied is to consider if the increase in overall disease burden based on change in non-measurable disease is comparable in magnitude to the increase that would be required to declare PD for measurable disease. Examples include an increase in a pleural effusion from ‘trace’ to ‘large’ or an increase in lymphangitic disease from localized to widespread.

#### **11.1.4      New lesions**

The appearance of new malignant lesions denotes disease progression.

- The finding of a new lesion should be unequivocal (i.e., not attributable to differences in scanning technique, change in imaging modality or findings thought to represent something other than tumor, especially when the patient’s baseline lesions show partial or complete response).
- If a new lesion is equivocal, for example because of its small size, continued therapy and follow-up evaluation will clarify if it represents truly new disease. If repeat scans confirm there is definitely a new lesion, then progression should be declared using the date of the initial scan.
- A lesion identified on a follow-up study in an anatomical location that was not scanned at baseline is considered a new lesion and disease progression.

Cytology and Histology: if the measurable disease is restricted to a solitary lesion, its neoplastic nature should ideally be confirmed by cytology or histology. These techniques can be used to differentiate between PR and CR in rare cases.

The cytological confirmation of the neoplastic origin of any effusion that appears or worsens during treatment when the measurable tumor has met criteria for response or stable disease is mandatory to differentiate between response, stable disease, and progressive disease.

#### **11.1.5      Evaluation of response**

Evaluation of Best Overall Response: the best overall response recorded from the start of the treatment until disease progression/recurrence (taking as reference for progressive disease the smallest measurements recorded since the treatment started). In general, the patient’s best response assignment will depend on the achievement of both measurement and confirmation criteria.

Table 11-1-5-1 provides a summary of the overall response status calculation at each time point for patients who have measurable disease at baseline.

**Table 11-1-5-1. Evaluation of best overall response in patients with measurable disease**

Target Lesions	Non-target Lesions	New Lesions	Overall Response
CR	CR	No	CR
CR	Non-CR/Non-PD	No	PR
CR	Inevaluable	No	PR
PR	Non-PD/or not all evaluated	No	PR
SD	Non-PD/or not all evaluated	No	SD
Not all evaluated	Non-PD	No	Inevaluable
PD	Any	Yes or No	PD
Any	PD	Yes or No	PD
Any	Any	Yes	PD

Note: Patients with a global deterioration of health status requiring discontinuation of treatment without objective evidence of disease progression at that time should be reported as “symptomatic deterioration”. Every effort should be made to document the objective progression even after discontinuation of treatment.

In some circumstances it may be difficult to distinguish residual disease from normal tissue. When the evaluation of complete response depends upon this determination, it is recommended that the residual lesion be investigated (fine needle aspirate/biopsy) before confirming the complete response status.

When patients have non-measurable (therefore non-target) disease only, Table 11-1-5-2 is to be used.

**Table 11-1-5-2. Evaluation of best overall response in patients with non-measurable disease**

Non-target lesions	New lesions	Overall response
CR	No	CR
Non-CR/non-PD	No	Non-CR/non-PD
Not all evaluated	No	Inevaluable
Uequivocal PD	Yes or no	PD
Any	Yes	PD

Inevaluable designation: When no imaging/measurement is done at all at a particular time point, the patient is not evaluable at that time point. If only a subset of lesion measurements are made at an assessment, usually the case is also considered not evaluable at that time point, unless a convincing argument can be made that the contribution of the individual missing lesion(s) would not change the assigned time point response. This would most likely happen in the case of PD.

## 11.2 Guidelines for Evaluation of Measurable Disease

The same method of assessment and the same technique should be used to characterize each identified and reported lesion at baseline and during follow-up. CT is the best currently available and reproducible method to measure lesions selected for response assessment. MRI is also acceptable in certain situations (e.g., for body scans but not for lung). Lesions on a chest X-ray may be considered measurable lesions if they are clearly defined and surrounded by aerated lung. However, CT is preferable. Ultrasound (US) should not be used to measure tumor lesions.

Clinical lesions will only be considered measurable when they are superficial and  $\geq 10$  mm in diameter as assessed using calipers. For the case of skin lesions, documentation by color photography, including a ruler to estimate the size of the lesion, is recommended. Tumor markers alone cannot be used to assess response. If markers are initially above the upper normal limit, they must normalize for a patient to be considered in complete response. Cytology and histology can be used in rare cases (e.g., for evaluation of residual masses to differentiate between Partial Response and Complete Response or evaluation of new or enlarging effusions to differentiate between Progressive Disease and Response/Stable Disease). Use of endoscopy and laparoscopy is not advised. However, they can be used to confirm complete pathological response.

## 11.3 Confirmation Measurement/Duration of Response

Confirmation: To be assigned a status of confirmed PR or CR, changes in tumor measurements must be confirmed by repeat studies that should be performed no less than 4 weeks after the criteria for response are first met. In the case of SD, follow-up measurements must have met the SD criteria at least once after study entry at a minimum interval of 6 weeks. Progression of disease should be verified in cases where progression is equivocal. If repeat scans confirm PD, then progression should be declared using the date of the initial scan. If repeat scans do not confirm PD, then the subject is considered not to have progressive disease per RECIST 1.1.

Duration of Overall Response: The duration of overall response is measured from the time measurement criteria are met for CR/PR (whichever is first recorded) until the first date that recurrent or progressive disease is objectively documented (taking as reference for progressive disease the smallest measurements recorded since the treatment started).

The duration of overall complete response is measured from the time measurement criteria are first met for CR until the first date that recurrent disease is objectively documented.

Duration of Stable Disease: Stable disease is measured from the start of the treatment until the criteria for progression are met, taking as reference the smallest measurements recorded since the treatment started.

Progression Free Survival (PFS): PFS is defined as the time from the date of first study treatment to the date of the first documented disease progression or death due to any cause. If a patient has not progressed or died at the date of the analysis cut-off or when he/she receives any further anti-cancer therapy, PFS is censored at the time of the last tumor assessment before the cut-off or the anti-cancer therapy date.

Time to Treatment Failure: Time from administration of the initial dose of treatment until study discontinuation for any reason (e.g. disease progression, toxicity, death, withdrawal of consent).

## **12. STATISTICAL CONSIDERATIONS**

### **12.1 Study Design**

This will be a prospective, single-institution, open-label, phase II clinical trial.

### **12.2 Sample Size/Accrual Rate**

For our primary endpoint, based on historical data and taking into account a mixed population of first-line versus beyond-first-line treatment patient population, we estimate response rate of 30% with standard platinum-based chemotherapy ( $H_0:p=0.30$ ). We hypothesize that FOLFIRINOX will have a response rate of 50% ( $H_1:p=0.50$ ). Using an alpha error of 0.10 and a beta error (1 minus power) of 0.20, based on the Simon two stage design, we estimate that we will need 28 evaluable patients to complete this trial. For the stage 1 part of this trial, 12 patients will be enrolled. If 3 or fewer patients achieve ORR, the trial will be stopped. If 4 or more patients achieve ORR, another 16 patients will be enrolled. By the end of the trial, if 11 or fewer patients achieve ORR, this trial will be considered a failure and no further investigation is warranted. We estimate that accrual will take 2 to 3 years. Primary objective will be evaluated after stage 1 and after stage 2, once the sample size is achieved. Patients who consent for the trial but do not receive any dose of treatment will be considered dropouts and will be replaced.

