## **6.4 Duration of Follow-Up**

Patients who discontinue chemotherapy prior to progression will continue to undergo scans every 8 weeks in order to evaluate for progression-free survival. Patients who discontinue treatment will continue to be monitored for overall survival via visits or phone calls at roughly 3 month intervals unless they specifically decline such follow-up.

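### Does the stage-1 futility rule in section 12.2 need a stated data cutoff and an explicit accrual hold?

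*Combined protocol and SAP*

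**What the plan says.** Section 12.2 sets a Simon two-stage design with a null response rate of 0.30, a target of 0.50, alpha 0.10 and beta 0.20, in 28 evaluable patients (12, then 16). The stage-1 boundary is explicit: "If 3 or fewer patients achieve ORR, the trial will be stopped", and "If 4 or more patients achieve ORR, another 16 patients will be enrolled". The timing statement is "Primary objective will be evaluated after stage 1 and after stage 2, once the sample size is achieved"; the synopsis says the same without the last clause. On duration, "We estimate that accrual will take 2 to 3 years".

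The response definitions are elsewhere. Section 11.1.5 takes "the best overall response recorded from the start of the treatment until disease progression/recurrence". Under section 11.3, "changes in tumor measurements must be confirmed by repeat studies that should be performed no less than 4 weeks after" the response criteria are first met. Section 10 schedules scans every 8 weeks and, when treatment slips, "efforts will be made to maintain scans at every 8 week +/- 2 week intervals regardless of the cycle number". Section 6.4 adds: "Patients who discontinue chemotherapy prior to progression will continue to undergo scans every 8 weeks in order to evaluate for progression-free survival".

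No section gives a minimum follow-up, scan number or cutoff date for the first 12 patients, and none says in so many words that enrolment pauses.

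**The concern.** The two stage-1 results mature at different speeds. A decision to continue is known at the fourth confirmed response. A decision to stop is certain only when 9 of the 12 can no longer respond. If best response is open until progression and scanning goes on after chemotherapy ends, a patient with stable disease stays undecided with no end date.

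Two consequences would follow. If accrual is held, the trial could be closed for months with the answer pending. If it is not held, patients are enrolled past the 12th before the futility result, and the saving from stage 1 shrinks. A third risk lies in reading the timing statement literally. A look at the 12th enrolment would come before that patient's first 8-week scan, and counting unassessed patients as non-responders would stop an effective regimen too often.

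**Working it through.** **1. The plan's own figures.** From section 12.2: n1 = 12, stop at 3 or fewer; n = 28, failure at 11 or fewer.

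- P(stop | p) = P(Bin(12, p) ≤ 3) = 0.4925 at p = 0.30 and 299/4096 = 0.0730 at p = 0.50.
- P(success | p) = Σ over x = 4 to 12 of P(Bin(12, p) = x) × P(Bin(16, p) ≥ 12 − x) = 0.0954 at 0.30 (alpha) and 0.8020 at 0.50 (power).
- E(N | 0.30) = 12 + (1 − 0.4925) × 16 = 20.12.

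The stated alpha and power hold, and this is the minimax design for those inputs.

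**2. The literal early look.** If k of the 12 are undetermined and counted as non-responders at stage 1 only, P(stop | 0.50) = P(Bin(12 − k, 0.50) ≤ 3). This is 0.113, 0.172 and 0.254 for k = 1, 2 and 3, and overall power is 0.778, 0.738 and 0.675. That would matter, but the plan does not support the reading. The design counts evaluable patients, and section 11.1.5 treats a patient with no imaging at a time point as not evaluable then, not as a non-responder.

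**3. The wait if counting runs strictly to progression.** Inputs: 28 patients in 104 or 156 weeks, so one per 3.71 or 5.57 weeks, evenly spaced; p = 0.30; non-responder progression-free survival (PFS) exponential, with an assumed median of 2, 3 or 4 months; progression seen at the next 8-week scan; stop certain at the 9th closed non-responder. Results are from a simulation of 300,000 trials per setting, among trials that stop, in weeks after the 12th start. The last two columns assume no hold: E(N | 0.30) = 20.12 + 0.4925 × mean number enrolled beyond the 12 (at most 16). The cutoff closes each patient at week 24.

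| Accrual, PFS median | Median wait | 90th percentile | P(>24 weeks) | Median wait with cutoff | E(N), no cutoff | E(N), cutoff |
|---|---|---|---|---|---|---|
| 2 years, 2 months | 16 | 37 | 0.26 | 12 | 22.6 | 21.7 |
| 2 years, 3 months | 26 | 58 | 0.55 | 16 | 24.0 | 22.0 |
| 2 years, 4 months | 38 | 81 | 0.76 | 17 | 25.2 | 22.2 |
| 3 years, 2 months | 10 | 32 | 0.18 | 8 | 21.5 | 21.0 |
| 3 years, 3 months | 21 | 53 | 0.42 | 13 | 22.4 | 21.2 |
| 3 years, 4 months | 32 | 74 | 0.63 | 13 | 23.4 | 21.3 |

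The 4-month rows are pessimistic. Section 1.2 reports 4 months for all platinum-etoposide patients, including the 31% who responded. If responders have a median of R months (assumed 6 to 12), the non-responder median m solves 0.31 × 2^(−4/R) + 0.69 × 2^(−4/m) = 0.50. This gives m ≈ 3.4 for R = 6 and 2.8 for R = 12, so the 3-month rows fit best.

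**4. How often a wait arises.** A response seen at week 8 can be confirmed at week 12 (the 4-week minimum) or at the week-16 scan. When the 12th patient starts, 8 (2-year accrual) or 9 (3-year) of the 12 are past week 12, and 7 or 9 are past week 16. The chance of fewer than 4 confirmed responses in hand is then:

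- p = 0.50, week 12: P(Bin(8) ≤ 3) = 0.363, P(Bin(9) ≤ 3) = 0.254. Week 16: 0.500 and 0.254.
- p = 0.30, week 12: 0.81 and 0.73. Week 16: 0.87 and 0.73.

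These assume that every response is first seen at week 8; later responses raise them.

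**5. What a cutoff costs.** Suppose a fraction q of responses come too late for the stage-1 count but still count among the 28. The stage-1 response probability becomes p(1 − q).

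- q = 0.05: P(stop | 0.50) = 0.100, power 0.785, alpha 0.092.
- q = 0.10: P(stop | 0.50) = 0.135, power 0.761, alpha 0.087.

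A 24-week hold would add 24/104 = 23% to a 2-year accrual or 24/156 = 15% to a 3-year one.

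**The case for a change.** The best case for a change is that full assessment has no stated end and a few sentences would supply one. At a true rate of 0.30 about half of trials should stop at stage 1, and that protection is the reason for two stages. With neither a cutoff nor a hold, the expected sample size could rise from 20.1 to 22.4 to 24.0 (3-month rows), giving back a good part of the saving. With a hold, 42% to 55% of stopping trials would wait more than 24 weeks on a strict count.

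It stands that the text is silent on both points and that a strict count can run long. It does not follow that the plan requires that count. Section 11.1.5 defines each patient's best response; it does not say that the interim count waits for every stable patient to progress. Section 11.3 says when stable disease may be assigned (after at least 6 weeks), and section 12.4 summarises best response in four categories, so a patient can be classified at an interim look. Section 6.4 gives progression-free survival as the reason for scans after chemotherapy. The planned course is up to 12 two-week cycles, with tumour measurements at cycles 5, 9 and 12. That gives a natural horizon near 24 weeks, although treatment and scanning may go on longer.

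**Conclusion.** No change to the plan is called for. The silence is a gap that the team can fill sensibly: assess the 12 through confirmation, open stage 2 at the fourth confirmed response, and otherwise wait, as the conditional wording of section 12.2 implies. On that reading alpha is 0.095 and power 0.802, and the boundaries stand.

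A written cutoff is a trade, not a clear gain. Without a hold it saves 1.2 to 2.0 expected patients at p = 0.30 (3-month rows: 22.4 − 21.2 and 24.0 − 22.0), or 0.5 to 3.0 over all rows. With a hold it shortens the median wait from 21 to 26 weeks to 13 to 16. Against that, it takes power below 0.80 and raises the chance of wrongly stopping at p = 0.50 from 0.073 to 0.100 to 0.135 if 5% to 10% of responses come late. Whether to pause accrual is likewise a choice between calendar time and patients enrolled before the futility result.

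The waits rest on assumed non-responder progression, even accrual and 8-week scans; the power cost rests on the assumed late fraction. The documents give neither the non-responder progression nor the late fraction.
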